## **B. Adverse Events**

Adverse events will be coded using MedDRA version 24.1. AEs are graded using the National Cancer Institute (NCI) Common Terminology Criteria for Adverse Events (CTCAE) Version 5.0.

A treatment-emergent AE (TEAE) is defined as AEs that first occurred or worsened in severity after the first administration of the study treatment (RXC004 or Nivolumab) and within 30 days of last dose of RXC004 in the case of Module 1 and Module 3 and within 90 days of last dose of Nivolumab for Module 2.

If relationship to RXC004 or Nivolumab is missing, the event will be conservatively treated as related to the corresponding study treatment. Missing CTCAE grade will be summarized as separate category.

All AEs will be listed by module, dose cohort and patient, detailing the verbatim term given by the investigator, the preferred term (PT), system organ class (SOC), onset date, stop date, CTCAE grade, relationship to RXC004, relationship to Nivolumab (Module 2 only), action taken with RXC004, action taken with Nivolumab (Module 2 only), other action taken, dose limiting toxicity (Y/N), caused by disease progression (Y/N) and seriousness. Dose limiting toxicity.

An overall AE summary will be present by the number and percent of patients for each module separately with the following:

- All AEs
- All TEAEs
- Dose limiting toxicity (DLTs) (Module 1 and 2 only)
- RXC004-related TEAEs

- Any TEAE of CTCAE of grade 3 or higher
- Any TEAE of CTCAE of grade 3 or higher related to RXC004
- Nivolumab-related TEAEs (Module 2 only)
- Any TEAE of CTCAE of grade 3 or higher related to Nivolumab (Module 2 only)
- Serious AEs
- RXC004-related SAEs
- Nivolumab-related SAEs (Module 2 only)
- TEAEs leading to RXC004 withdrawal
- TEAEs leading to Nivolumab withdrawal
- TEAEs leading to RXC004 reduction
- RXC004 related adverse event leading to death
- Nivolumab-related adverse event leading to death (Module 2 only)
- TEAEs leading to RXC004 interruption
- TEAEs leading to Nivolumab interruption
- AEs leading to death

The following AE summaries will be produced by system organ class (alphabetical order) and preferred term (descending order of the overall frequency) for each module separately:

- All TEAEs
- Serious AEs
- Grade 3 or higher TEAEs
- TEAEs leading to RXC004 withdrawal. This subset includes TEAEs with an Action Taken with RXC004 of “Drug Permanently Withdrawn” on the AE form.
- TEAEs leading to RXC004 reduction. This subset includes TEAEs with an Action Taken with RXC004 of “Dose reduced” on the AE form
- TEAEs leading to RXC004 interruption. This subset includes TEAEs with an Action Taken with RXC004 of “Dose interrupted” on the AE form
- TEAEs leading to Nivolumab withdrawal (Module 2 only). This subset includes TEAEs with an Action Taken with Nivolumab of “Drug Permanently Withdrawn” on the AE form.
- TEAEs leading to Nivolumab interruption (Module 2 only). This subset includes TEAEs with an Action Taken with Nivolumab of “Dose interrupted” on the AE form
- TEAEs related to RXC004. This table will include TEAEs with a drug relationship of “Possibly Related” or “Probably Related” to RXC004.
- TEAEs related to Nivolumab (Module 2 only). This table will include TEAEs with a drug relationship of “Related” to Nivolumab.
- SAEs related to RXC004
- SAEs related to Nivolumab (Module 2 only)
- Grade 3 or higher TEAEs related to RXC004
- Grade 3 or higher TEAEs related to Nivolumab (Module 2 only)
- AEs leading to death

- AEs considered as dose-limiting toxicity (DLT) (Module 1 and 2 only)
- TEAEs by maximum CTCAE grade
- TEAE by PT
- Treatment Related TEAE by PT.

At each level of summarization, a patient will be counted once if he/she reported one or more events. The maximum CTCAE grade will be taken for the purposes of the summaries by grade.

In addition, all deaths as collected on the Death eCRF page will be present in a data listing.

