## 4 SAFETY – CORE

### 4.1 Definitions of Adverse Events and Serious Adverse Events

The Investigator is responsible for recording all AEs observed during the study (from time of signed consent, washout, treatment, and follow-up) period.

Definition of AE: An AE is any new untoward medical occurrence or worsening of a pre-existing medical condition in a subject or clinical investigation subject administered a pharmaceutical product and which does not necessarily have a causal relationship with this treatment.

Treatment-emergent adverse events: An AE occurring after dosing and within 30 days of last dose.

Definition of Serious Adverse Event (SAE): An SAE, experience or reaction, is any untoward medical occurrence (whether considered to be related to study drug or not) that at any dose:

- Results in death.
- Is life-threatening (the subject is at a risk of death at the time of the event; it does not refer to an event which hypothetically might have caused death if it were more severe).
- Requires inpatient hospitalization or prolongation of existing hospitalization: Hospitalizations are defined as initial or prolonged admissions that include an overnight stay. Hospitalization or prolonged hospitalization for technical, practical or social reasons, in the absence of an adverse event is not an SAE. Hospital admissions and/or surgical operations planned before or during a study are not considered AEs if the illness or disease existed before the subject was enrolled in the study, provided that it did not deteriorate in an unexpected way during the study.
- Results in persistent or significant disability/incapacity.
- Is a congenital abnormality/birth defect.
- Other: Medically significant events, which do not meet any of the criteria above, but may jeopardize the subject and may require medical or surgical intervention to prevent one of the other serious outcomes listed in the definition above. Examples of such events are blood dyscrasias (e.g. neutropenia or anemia requiring blood transfusion, etc.) or convulsions that do not result in hospitalization.

An Adverse Drug Reaction (ADR) is defined as all noxious and unintended responses to a medicinal product related to any dose. An Unexpected Adverse Drug Reaction is defined as any adverse reaction, the nature of which is not consistent with the applicable product information.

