### 5.3.7 Dose Modifications

RXC004 dose reduction and interruption are permitted. Nivolumab dose reduction is not permitted but dose interruption/delay is permitted.

RXC004 may be dose interrupted (withheld) for up to 14 days until a clinically significant (any grade) and/or a grade  $\geq 3$  related adverse event resolves to baseline or  $\leq$  grade 1. Patients that experience a RXC004 related adverse events that do not resolve to baseline or  $\leq$  grade 1 after 14 days of dose interruption/delay despite appropriate treatment must be discussed with Sponsor, before re-starting RXC004.

Adverse events that are assessed as being causally related nivolumab should be managed as per the Nivolumab Toxicity Management and Dose Modification Guidelines (Appendix 8). If either agent alone is interrupted or discontinued for a related-AE the other agent (nivolumab or RXC004) may be continued if the patient is judged (by the investigator) to be receiving clinical benefit. If a patient continues in the study on nivolumab alone, this treatment may be continued for a maximum of 12 months in total.

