**Table 6 Module 2 Dose Interruption and Stopping Criteria**

Event	Action

Colitis events            (e.g. Colitis, ileitis, enterocolitis etc)
	

Grade 1
	
If receiving RXC004, either as monotherapy or in combination with nivolumab;            Reduce RXC004 to a lower dose and manage as per Appendix 5 (and Appendix 8 if applicable)

Grade 2
	
If receiving RXC004, either as monotherapy or in combination with nivolumab            Interrupt RXC004. Manage as per Appendix 5 and Appendix 8 if applicable. When event has resolved to Grade <math>\leq 1^a</math> and steroids tapered to <math>\leq 10</math> mg of prednisone per day (or equivalent), resume RXC004 at a lower dose and nivolumab (if applicable) at 480 mg once every month.            If event re-occurs after re-starting study treatment, then RXC004 and nivolumab (if applicable) should be permanently discontinued.

Grade 3
	
If receiving RXC004 monotherapy;            Interrupt RXC004. Manage as per Appendix 5 When event has resolved to Grade <math>\leq 1^a</math> and steroids tapered to <math>\leq 10</math> mg of prednisone per day (or equivalent), resume RXC004 at a lower dose.            If event re-occurs after re-starting study treatment, then RXC004 should be permanently discontinued.              If receiving RXC004 in combination with nivolumab; permanently discontinue both agents and manage as per Appendix 5 and Appendix 8.

Event	Action
Grade 4	If receiving RXC004, either as monotherapy or in combination with nivolumab; Permanently discontinue study treatment (both agents if applicable). Manage as per Appendix 5 and Appendix 8
Dysgeusia events	
Grade 1 or 2	RXC004 related; Consider dose reduction, depending on clinical symptoms Manage as per Appendix 6 Interrupt RXC004 treatment if dysgeusia is associated with >5kg weight loss from baseline
Grade 2 associated with a 10-20% decrease in body weight	RXC004 related; Manage as per Appendix 6 Reduce RXC004 to a lower dose.
Grade 2 associated with a >20% decrease in body weight	RXC004 related; Manage as per Appendix 6 Permanently discontinue RXC004. Nivolumab can continue if clinical benefit is judged by investigator for a maximum of 12 months total treatment.
Other adverse events	
Any event that meets discontinuation criteria for nivolumab (see Appendix 8)	Permanently discontinue nivolumab. RXC004 can continue, if clinical benefit is judged by investigator.

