### 5.3.10 Exploratory Assessments

The circulating soluble factors and PBMC pharmacodynamic samples (all sites) will be obtained at C0D1 (prior to first dose) and on C1D15 and Day 1 of each cycle thereafter. These samples may be used to examine gene and protein expression changes, including measurement of inflammatory markers. Fresh whole blood (from selected sites of close proximity) will be obtained at C0D1 (prior to first dose), and pre-dose at C1D15 and C2D1. Fresh whole blood may be stained for cell surface markers to identify immune cell populations present in the circulation before and after treatment. Circulating tumour DNA (ctDNA) and RNA (ctRNA) will be collected pre-dose at C0D1, post-dose on C1D15 and Day 1 of each subsequent cycle and at treatment discontinuation. Analysis of total amounts and/or tumour mutations (including Wnt pathway aberrations) in ctDNA samples may be evaluated and correlated to patient response.

## 5.4 Module 3

Module 3 will investigate the PK, Wnt pathway inhibition, incidence/severity of Wnt pathway related adverse events and anti-tumour activity of RXC004 when given at 2 different intermittent dosing schedules, in a selected group of patients with Wnt ligand dependent advanced solid tumours.

Following the completion of Module 1, the 2mg QD dose was selected as the recommended starting dose for Phase 2 studies, with options of interruptions and dose reductions to manage potential toxicities. The most frequently occurring treatment related AEs in module 1 (all doses) were fatigue (52%), nausea (44%), decreased appetite (40%), dysgeusia (40) and

vomiting (24%). The median RXC004 exposure in Module 1 was approximately 7 weeks so these adverse events were generally observed during the first two treatment cycles. Of the observed adverse events, only dysgeusia, a known on-target toxicity of Wnt pathway inhibitors, was observed to be dose-related and 4 out of 6 patients in the 2mg cohort reported dysgeusia within the first 2 treatment cycles. Module 3 will explore whether intermittent dosing schedules have the potential to deliver clinical anti-tumour activity in selected patients with Wnt ligand dependent tumours and whether intermittent dosing, giving short treatment breaks, has the potential to reduce incidence of treatment related toxicities such as dysgeusia. If so, an intermittent dosing schedule could be a future alternative to dose reduction in the management of treatment related adverse events.

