### 9.2 Statistical Methods

All analyses, summaries, and listings will be performed using SAS® software (version 9.3 or higher). Modules will be summarized separately.

A baseline assessment will be defined as the last assessment performed prior to the first dose of study treatment. While many of these assessments will be performed on the day of the first dose, others will be performed during screening. If a patient is missing an assessment typically performed on the day of the first dose, screening values may be substituted as baseline.

Patient disposition, demographics, and baseline characteristics will be summarised using descriptive statistics.

In general, all efficacy, safety, and PK variables will be summarised using descriptive statistics. Continuous variables will be summarised by descriptive statistics (sample size [n], mean, standard deviation [SD], median, minimum and maximum). Categorical variables will be summarised in frequency tables (n, frequencies, and percentages). Individual subject data will be presented in listings. Missing data will not be imputed unless otherwise stated

The study data from each module will be analyzed and reported based on all patient data up to the time when all module patients have completed at least 6 cycles of treatment or have discontinued study treatment. Data will be listed, summarized, and analyzed by dose level and overall.

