## 9.6 Safety

### 9.6.1 Adverse Events

Treatment-emergent adverse events are defined as AEs that first occurred or worsened in severity after the first administration of the study drug and within 30 days of last dose of RXC004 in the case of module 1 and within 90 days of last dose of nivolumab for module 2. Adverse event summaries will include incidence of treatment-emergent AEs by MedDRA preferred term and system organ class, SAEs including deaths, AEs that led to study drug discontinuation, AEs leading to death, treatment related AEs and AEs by maximum severity..

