- i Consenting patients will have a 10 mL blood sample taken for preparation of a germ-line DNA sample at Screening (recommended time-point only).
- j CT (preferred) or MRI, each preferably with IV contrast. It is strongly recommended to maintain use of the same imaging modality (CT or MRI), acquisition protocol, facility and scanner across all imaging time points per patient. Note that where there is a rationale for assessment of bone lesions that develop after study start, these assessments will be performed as part of the CT or MRI assessment and will not require additional radiological bone scan assessment. Additional scans may be performed to confirm a Complete Response (CR) or Partial Response (PR) or disease progression (PD) as per appropriate response assessment guidelines. Any requirement for confirmatory scans will typically be performed at the next protocolled assessment time point. Other assessments e.g. whole body MRI or PET, are not protocol mandated, but may be performed as clinically indicated and at request of Investigator.
- k 480mg IV infusion over 60 minutes, q4w +/- 3 days, unless an infusion needs to held due to an adverse event. Results for chemistry, haematology and thyroid function labs must be available before commencing an infusion (within 3 days) and reviewed by the treating physician or Investigator prior to dosing. If a patient continues in the study on nivolumab alone, this treatment may be continued for a maximum of 12 months in total.
- l Follow up assessments should be performed 30 days after discontinuation of IP and 90 days after last dose of nivolumab
- m T3 and T4 will only be measured if TSH is abnormal or if there is clinical suspicion of an AE related to the endocrine system
- n For patients with Wnt ligand dependent tumours only (RNF43/RSPO aberrations or biliary/thymus cancers).

- o All patients must receive denosumab before first dose of RXC004. 120 mg sc denosumab should be administered approximately once every month from C0D1 until RXC004 discontinuation. Investigators may delay subsequent denosumab doses until the next scheduled visit providing that there is no significant increase in  $\beta$ -CTX compared to baseline, according to Investigator judgement

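### Module 2's TEAE window closes 90 days after the last nivolumab dose and ignores RXC004, so late events on RXC004 given alone drop out of the TEAE tables

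*SAP*

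**What the plan says.** SAP IX.B opens the TEAE window at the first dose of either drug. For Modules 1 and 3 it closes 30 days after the last RXC004 dose. For Module 2 it closes "within 90 days of last dose of Nivolumab for Module 2". Protocol 9.6.1 agrees for Module 2: "within 90 days of last dose of nivolumab for module 2". Neither adds a rule that takes the later of two dates.

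Protocol 4.1 has a different, general definition: "An AE occurring after dosing and within 30 days of last dose". It does not say which drug's last dose is meant.

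The protocol provides for the two drugs to stop at different times. Section 5.3.7 says that if one is interrupted or stopped for a related event, "the other agent (nivolumab or RXC004) may be continued if the patient is judged" by the investigator to be benefiting. Table 6 says, for events that meet the nivolumab discontinuation criteria: "Permanently discontinue nivolumab. RXC004 can continue, if clinical benefit is judged by investigator". The 12-month cap in 5.3.7 applies to nivolumab alone; none is stated for RXC004 alone.

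The Module 2 schedule (Appendix 2, footnote l) has two follow-up anchors: "Follow up assessments should be performed 30 days after discontinuation of IP and 90 days after last dose of nivolumab".

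**The concern.** The window opens on either drug but closes on one. If nivolumab stops and RXC004 continues, the window can close while the patient is still taking the investigational drug. Later events are recorded but are not TEAEs.

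Safety and tolerability is the primary objective, and the TEAE tables are its main summary by event term. Those affected are: all TEAEs, Grade 3 or higher, RXC004-related, maximum grade, by preferred term, and TEAEs leading to RXC004 withdrawal, reduction or interruption. The error runs one way, towards under-counting later RXC004 toxicity.

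Two further points follow from the same rule:

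- A Module 2 patient who received only the Cycle 0 dose of RXC004 is in the Safety Population (SAP VI.J.1) but has no last nivolumab date, so the end of the window is undefined.
- SAP IX.A measures RXC004 exposure to the last RXC004 dose, so the exposure tables count time that the TEAE tables leave out.

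**Working it through.** The plan gives no figure to reproduce. The check is date arithmetic.

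**Inputs**

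- Nivolumab every 28 days from Cycle 1 Day 1, taken as Day 1 (protocol 5.3): infusions on Days 1, 29, 57, 85 and 113.
- Window end = last nivolumab day + 90 (SAP IX.B).
- RXC004 follow-up of 30 days, the SAP's own interval for Modules 1 and 3.
- Illustrative RXC004 duration: six cycles, 6 × 28 = Day 168. Protocol 9.2 reports a module once "all module patients have completed at least 6 cycles of treatment or have discontinued study treatment". Continuing to Day 168 is an assumption; the documents give no Module 2 exposure times.

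**Formulas**

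- On-drug days outside = max(0, 168 − window end)
- On-drug plus follow-up days outside = max(0, 168 + 30 − window end) = max(0, 198 − window end)

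| Last infusion | Day | Window ends | On-drug days outside | Share of 168 | Including 30-day follow-up |
|---|---|---|---|---|---|
| 1 | 1 | 91 | 168 − 91 = 77 | 45.8% | 198 − 91 = 107 |
| 2 | 29 | 119 | 168 − 119 = 49 | 29.2% | 198 − 119 = 79 |
| 3 | 57 | 147 | 168 − 147 = 21 | 12.5% | 198 − 147 = 51 |
| 4 | 85 | 175 | 0 | 0% | 198 − 175 = 23 |
| 5 | 113 | 203 | 0 | 0% | 0 |

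**Thresholds.** On-drug days are lost only if RXC004 runs more than 90 days past the last infusion, that is, more than 90 − 28 = 62 days past the first missed infusion date. Follow-up days are lost only if it runs more than 90 − 30 = 60 days past the last infusion.

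**Sensitivity to duration**, with nivolumab stopped after infusion 1:

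- RXC004 to week 16 (Day 112): 112 − 91 = 21 on-drug days outside.
- RXC004 to week 52 (Day 364): 364 − 91 = 273 on-drug days outside.

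**A concrete case.** Appendix 2 schedules a DXA scan at Cycle 7, whose Day 1 is 6 × 28 + 1 = Day 169. Table 6 makes a loss of bone mineral density of 7% or more a reason to stop RXC004, and protocol 4.1 makes such a finding a reportable AE when it causes discontinuation. If nivolumab ended with infusion 1, 2 or 3, Day 169 is past the window end (Day 91, 119 or 147), and the event would be absent from the table of TEAEs leading to RXC004 withdrawal.

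**Could another passage repair the rule?** The general definition in protocol 4.1 names no drug and conflicts with the module-specific one. If read as the last dose of any study drug, it would keep patients on RXC004 in the window but cut nivolumab's 90 days to 30. Footnote l governs follow-up visits, not which events count as TEAEs. Neither supplies the missing RXC004 anchor.

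**The case against.** The case on the other side is that the effect is narrow.

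- **Other outputs show much of the same information.** RXC004 dose changes with reasons (SAP IX.A), treatment discontinuations with reasons (VII.C), graded laboratory shift tables (IX.C), β-CTX summaries (IX.K) and DXA listings (IX.L) are not limited to TEAEs. Nor are the line for all AEs, the SAE, death and DLT outputs, or the AE listing. This stands as mitigation: what is lost is chiefly late, non-serious, non-fatal events. But none of these outputs restores the missing counts by system organ class and preferred term.
- **The trigger is uncommon.** Several rules that stop nivolumab also stop RXC004: Grade 3 or 4 colitis on the combination, recurrent Grade 3–4 toxicity, and prolonged steroid or immunosuppressant use. A temporary hold followed by re-start moves the last-dose date forward. Module 2 plans only about 18 patients.
- **The illustration assumes long exposure.** Protocol 5.4 states: "The median RXC004 exposure in Module 1 was approximately 7 weeks". A patient treated for 7 weeks loses nothing. That figure is for monotherapy, but it is the only exposure evidence given. It supports reading the affected group as a minority, not as empty.
- **Amending the protocol costs more than a line of code.** This is fair. Changing the SAP derivation alone corrects the tables; the protocol wording can be aligned separately.
- **The Cycle 0-only case could fall back on protocol 4.1.** It could, but the SAP should say so.

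**Conclusion.** The concern holds. Followed as written, the plan excludes events on RXC004 alone from all TEAE-based tables once more than 90 days have passed since the last nivolumab dose. It can also exclude events in the 30 days after RXC004 stops, if RXC004 ran more than 60 days past that dose.

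In the six-cycle illustration the on-drug loss is 77, 49 or 21 days after a last infusion 1, 2 or 3, and none after infusion 4 or later. This assumes RXC004 to Day 168 and infusions on schedule. The number of patients affected is not in the documents and is probably small, but with about 18 patients split across dose cohorts, one or two missing events would visibly change a row.

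The MTD decision is unaffected, because it rests on Cycle 1 DLTs and SRC review. No hypothesis test is involved. This should be fixed before Module 2 is reported.

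**What to change.** In SAP IX.B, define a Module 2 TEAE as an event that starts or worsens after the first dose of either drug and up to the later of:

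- 30 days after the last RXC004 dose, and
- 90 days after the last nivolumab dose.

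If nivolumab was never given, use 30 days after the last RXC004 dose. Both intervals are the sponsor's own.

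Carry the same wording into protocol 9.6.1 and 4.1. As tidying, align the Module 2 post-treatment SAE window in 4.2, now tied to nivolumab only, with footnote l.

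**Cost.** The SAP change is a sentence and a line of derivation code. No new data are needed, because footnote l already schedules both follow-ups and AEs are collected at each cycle visit. TEAE counts may rise slightly. The protocol edits need an amendment. If only the SAP is changed, the study report should record the departure from 9.6.1.

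**A separate, minor point.** Protocol 4.1 allows causality to be recorded as unknown. SAP IX.B puts only possible and probable events in the RXC004-related TEAE table, yet counts missing causality as related. The SAP should state how unknown is handled; counting it as related would match the rule for missing.

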### **Relationship**

The causal relationship between the study medication and the AE has to be characterized as unrelated, unlikely, possible, probable or unknown (unable to judge).

Events can be classified as “unrelated” if there is not a reasonable possibility that the study medication caused the AE. An “unlikely” relationship suggests that only a remote connection exists between the study drug and the reported AE. Other conditions, including chronic illness, progression or expression of the disease state or reaction to concomitant medication, appear to explain the reported AE.

A “possible” relationship suggests that the association of the AE with the study medication is unknown; however, the AE is not reasonably supported by other conditions.

A “probable” relationship suggests that a reasonable temporal sequence of the AE with drug administration exists and, in the Investigator’s clinical judgment, it is likely that a causal relationship exists between the drug administration and the AE, and other conditions (concurrent illness, progression or expression of disease state or concomitant medication reactions) do not appear to explain the AE.

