### 5.2.6 Dose-Limiting Toxicity for Module 1 (RXC004 Monotherapy)

The DLT assessment period runs from the start of dosing with RXC004 (Cycle 0 Day 1) up to Cycle 1 Day 21 for patients enrolled in Module 1.

A DLT is defined as an AE or abnormal laboratory value that occurs from the first dose of study treatment up to Cycle 1 Day 21, assessed as unrelated to disease progression, intercurrent illness, or concomitant medications that despite optimal therapeutic intervention meets any of the following criteria:

1. Haematological toxicity that is:
  - CTCAE  $\geq$  Grade 4 present for more than 4 consecutive days
  - Grade 3 neutropenia (ANC  $\geq$  500 to  $<$  1000 cells/mm^3) of any duration accompanied by fever ( $\geq$  38.5°C) and/or systemic infection
  - Grade 3 thrombocytopenia (25,000 to  $<$  50,000/mm^3) with clinical evidence of bleeding
2. Any other confirmed haematological toxicity CTCAE  $\geq$  Grade 4 (a repeat may be required for confirmation of an isolated abnormality in the absence of clinical signs, symptoms or other abnormal investigations, i.e. a suspected spurious value)
3. Non-haematological toxicity CTCAE  $\geq$  Grade 3 including:

- Laboratory abnormalities that are considered clinically significant by the investigator (with or without clinical symptoms or signs)
  - QTc prolongation ( $> 500$  msec or 60 msec above baseline)
4. Any other toxicity that:
- Is greater than that at baseline, is clinically significant and/or unacceptable, and is judged to be a DLT by the SRC
  - Is a protocol defined stopping criterion and is suspected to be RXC004 related
  - Results in an interruption of dosing schedule of more than 14 days

A DLT excludes:

1. Inadequately treated  $\leq$ Grade 3 nausea and/or vomiting and  $\leq$ Grade 3 diarrhoea
2. Any toxicity clearly unrelated to RXC004 e.g. solely related to the disease or disease-related process under investigation
3. Isolated laboratory changes of any grade without clinical sequelae or clinical significance

The incidence and type of DLT-type toxicity emerging from treatment beyond Cycle 1 Day 21 will be taken into account by the SRC in determining dose-escalation steps.

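### The SAP's RXC004-related TEAE table leaves out events scored as unknown causality but counts events with no score at all

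*SAP*

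**What the plan says.** **The scale.** Protocol Section 4.1, under Relationship, requires each event's causality to be "characterized as unrelated, unlikely, possible, probable or unknown (unable to judge"). The text then describes four of the five levels. *Unknown* gets no description. No separate scale is given for nivolumab.

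**The RXC004 filter.** In SAP Section IX.B, the list of tables by system organ class and preferred term restricts the RXC004-related TEAE table to events with a "drug relationship of “Possibly Related” or “Probably Related” to RXC004".

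**The missing-data rule.** Earlier in SAP Section IX.B: "If relationship to RXC004 or Nivolumab is missing, the event will be conservatively treated as related to the corresponding study treatment".

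**The nivolumab filter.** The matching Module 2 table is defined by a "drug relationship of “Related” to Nivolumab".

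**Other related outputs.** SAP Section IX.B also lists related SAEs, related events of Grade 3 or higher, related events leading to death, and treatment-related TEAEs by preferred term. None of these has a stated filter.

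**The concern.** A blank field and an *unknown* score mean much the same thing: nobody has established whether the drug caused the event. The SAP resolves the first against the drug and says it does so to be conservative. Its filter resolves the second in the drug's favour and gives no reason. The event with no assessment enters the table, and the event with an inconclusive assessment does not.

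The boundary is also hard for investigators to apply consistently. The protocol's text for *possible*, which is counted, "suggests that the association of the AE with the study medication is unknown". Two investigators with the same doubt could choose *possible* and *unknown* and send identical events to opposite sides of the filter.

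Safety and tolerability is the primary objective of every module (Protocol Section 1.9.1). The protocol uses treatment-related rates to describe the tolerability of 2 mg (Section 5.4.3), and Module 3 asks whether intermittent dosing reduces treatment-related toxicity such as dysgeusia (Section 5.4). A rule that can move those rates in only one direction should be deliberate and stated.

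**Working it through.** The plan gives no figure to reproduce. The check is to pass every possible causality entry through the SAP's stated rules, and then to scale the effect of one affected patient.

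**Step 1. Each entry under the rules for the RXC004-related TEAE table**

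| Causality entry | Rule that applies | In the table? |
|---|---|---|
| Unrelated | not in the filter | no |
| Unlikely | not in the filter | no |
| Possible | in the filter | yes |
| Probable | in the filter | yes |
| Unknown | not in the filter; no other rule | **no** |
| Blank | missing-data rule | **yes** |

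The last two rows are the inconsistency.

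**Step 2. Direction.** Compared with treating *unknown* as the SAP treats a blank, the filter can remove patients from the numerator but cannot add any. The denominator does not change. The related rate therefore stays the same or falls.

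**Step 3. Size per affected patient.** The SAP counts a patient once at each level of summary. A rate changes only if the patient's events at that level include an *unknown* score and none that is possible, probable or missing. One such patient lowers the rate by 1/n.

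| Group | n (source) | 1/n |
|---|---|---|
| Module 3 arm | 6 (SAP Section IV.C) | 16.7 points |
| Module 2, all patients | about 18 (SAP Section IV.C) | 5.6 points |
| Module 1, largest cohort (1.5 mg) | 7 (Protocol Section 5.4.3) | 14.3 points |
| Module 1, smallest cohort of the restarted escalation (1 mg) | 3 (Protocol Section 5.4.3) | 33.3 points |

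The Module 3 figure assumes exactly six treated patients. Six is the target for evaluable patients, so an arm with more treated patients would show a smaller change. The single patient treated at 10 mg is left out of the table because a percentage from one patient means little.

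**Step 4. What cannot be computed.** The total effect is the number of affected patients divided by n. Neither document says how many events were scored *unknown*. If there were none, the effect is zero.

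**Step 5. Nivolumab.** The label *Related* is not one of the protocol's five levels. If the nivolumab field used that scale, possible and probable scores would not match the filter. If it is a separate related/not related field, the filter works as written. The eCRF is not among the documents, so only the mismatch in wording is established.

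**The case against.** **Unable to judge is an assessment, not missing data.** The missing-data rule was written for blanks, and the filter for recorded scores, so the two need not agree. This explains how the gap could arise but does not justify it. The only reason the SAP gives for counting blanks is conservatism, and that reason applies at least as well to a recorded *unknown*.

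**The form may not offer *unknown*.** This stands as a limit. The protocol requires the level, but the eCRF cannot be checked here. If the form omits it, the SAP should say so.

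**A separate row for *unknown* would serve as well.** The SAP does this for missing CTCAE grade. It would be transparent, but blanks would still count as related while *unknown* did not. Counting both and footnoting the numbers resolves the inconsistency and keeps the transparency.

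**No decision turns on this table.** Largely true. Escalation and the MTD rest on DLTs and Safety Review Committee review, and the SAP plans no hypothesis test (Section VI.H). The related-event tables are still a main description of a primary objective.

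A reader might also infer stronger points that the documents do not support:

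- *That these events vanish from safety reporting.* They remain in the all-TEAE tables, in the serious, Grade 3 or higher and dose-action tables where they qualify, and in a listing that shows the recorded relationship.
- *That the filter conflicts with the DLT counts.* A Module 1 DLT must be "assessed as unrelated to disease progression, intercurrent illness, or concomitant medications" (Protocol Section 5.2.6). An event with those explanations ruled out fits the protocol's description of *possible*, which the SAP counts. The Module 2 definition (Section 5.3.6) itself asks for a possible relationship. DLTs have their own flag, summary row and table.
- *That the nivolumab-related table would capture no scored event.* That assumes the nivolumab field carries the protocol scale. The SAP lists relationship to each drug separately, and nearby quoted labels are values on the AE form, so a separate field is quite plausible.
- *That rates already quoted, such as fatigue in 10/20 and dysgeusia in 6/20 patients at up to 2 mg, are too low.* Nothing shows that any *unknown* score affected them.

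**Conclusion.** The point holds for the RXC004-related TEAE table. By the stated rules, an event scored *unknown* is left out while an unscored event is counted. This contradicts the SAP's own conservative principle and can only lower the related rate. The size is 17 percentage points per affected patient in a six-patient Module 3 arm. The number of affected patients is not known and may be zero.

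The conclusion assumes that the AE form carries the protocol's five levels for RXC004 and that the filter is applied as written. Extending the filter to related SAEs, Grade 3 or higher events and deaths would be inference, because the SAP gives no definition for those outputs. That silence is a reason to supply one. For nivolumab, the documents establish only that the filter uses a label absent from the protocol's one causality scale.

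**What to change.** In SAP Section IX.B:

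1. Define RXC004-related as possible, probable, unknown (unable to judge) or missing.
2. Apply that one definition to every RXC004-related output: TEAEs, SAEs, Grade 3 or higher, leading to death, and by preferred term.
3. Footnote each such table with the number of events that enter through *unknown* and through missing scores, so that a reader can recover the narrower count.
4. For nivolumab, confirm which levels the eCRF field holds and state how *Related* maps to them.

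Apply this to Modules 2 and 3. SAP Section I says that the changes specific to those modules were made after the Module 1 database was locked, and that any deviation after lock will be documented in the study report. Any effect on Module 1 should be documented there. This also keeps an informal comparison of Module 3 with the Module 1 rates on a known footing.

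The cost is SAP wording and one derivation flag, with no new data. The downside is that related-event rates may look slightly less favourable.
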